#### 3.6.2 Registry Subjects

Patients that refuse ICD implantation will not be randomized and will be approached to sign consent for inclusion into a registry if they undergo catheter ablation without ICD. Basic demographics and medical history will be collected from registry subjects upon enrollment. Registry subjects will receive a phone contact and follow-up with clinic visits and device interrogation at 3, 6, 12, 18, 24, 30 and 36 months to check on their overall status. Due to the COVID19 global pandemic, China centers were shut down and complete access for patient follow-up will require an additional 6-12 months. Therefore, we are requesting one extra year extension for follow up due to these unanticipated circumstances. No statistical review or analysis was performed,

as follow-up remains incomplete as of April, 28th, 2020. Registry subjects will receive a phone contact and follow-up with clinic visits 30 and 36 months to check on their overall status

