#### **4.5.4 ICD Programming**

The ICD will be programmed to disable all therapies during mapping and ablation.

In the Note section of the device, type the following message:

PAUSE-SCD Trial subject. Please contact [physician or coordinator name] at [center name] at [center phone] before making any programming changes.

Protocol-mandated programmed settings should be confirmed after the device is enabled at the conclusion of ablation. VF zone of 230 bpm (ATP during charging) and VT zone 185 or 10 bpm slower than clinical VT (induced or spontaneous) with detection at 30/40 intervals. (ATPx3).

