### 4.7.1 Scheduled Visits

The following shall be evaluated at every visit:

- Assessment of AAD medication
- Assessment of anti-coagulation medication

- Assessment of Adverse Events
- ICD Interrogation and event printout
- An Echocardiogram will be performed at 6 months, 1 year, and 2 years if not already performed for routine clinical evaluation.

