### **9.2 Primary Endpoint**

The primary efficacy endpoint is defined as freedom from recurrent VT, cardiovascular rehospitalization, and all-cause mortality through a period of 2 years after the procedure (ablation) or randomization (standard medical therapy). Recurrent VT is defined as any appropriate ICD therapy (shock or ATP) or documented sustained monomorphic VT >30 seconds. Cardiovascular rehospitalization is defined as a hospital admission after the randomized procedure for heart failure, procedure-associated complication, or arrhythmia-related causes during the follow-up period.

Prespecified secondary endpoints include each of the individual components of the primary endpoint. Comparison of the ablation-only registry with the randomized patients will serve as an additional secondary outcome measure.

Prespecified subgroup analysis will be performed for patients with RV cardiomyopathy.

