### **9.3 Primary Endpoint Analysis**

The primary endpoint analysis will be a time to event analysis and account for censored observations for all randomized subjects. Intention to treat analysis will be used for this endpoint; the analysis will be “analyzed as randomized” regardless of the actual treatment patients receive during the follow-up period. Kaplan-Meier (1958) estimates of the primary endpoint and overall survival will be generated along with 95% confidence intervals for the median time to event or death (Brookmeyer and Crowley, 1982).(8,9) Log-rank test will be used to compare the hazard functions between the two groups. Cox (1972) regression models will be fit to assess and adjust for baseline covariates.(10) The median time to VT recurrence as well as the 95% confidence intervals will be reported for both groups. The event free survival probability as well as the 95% confidence intervals at the 24-month follow-up for both groups will be presented. Adverse events will be tabulated by type and level of severity and compared between groups using chi-square or Fisher exact tests.

Secondary analyses comparing outcomes in the ICD+ablation and ICD arms vs. the registry patients (ablation only) will be performed in a similar manner to those described above.

Interim analyses will be generated by the coordinating center annually. A Peto-Haybittle efficacy monitoring boundary will be used: if the p-value for the difference between groups is <0.001, early stopping of the trial will be considered. Using this monitoring bound, the p-value for statistical significance at the final analysis will remain at the nominal 0.05 level.

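### Secondary registry comparison only: recurrent VT is ascertained differently in registry patients, who have no ICD, than in the two ICD arms they are compared with

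*Combined protocol and SAP*

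**What the plan says.** Section 3.5.1 gives both randomized arms an ICD. Section 3.6.2 enters patients in the registry "if they undergo catheter ablation without ICD", and section 2.2 says the registry will assess how ablation performs with no ICD in the background.

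Section 9.2 defines the VT component: "Recurrent VT is defined as any appropriate ICD therapy (shock or ATP) or documented sustained monomorphic VT >30 seconds". The composite adds all-cause death and a "hospital admission after the randomized procedure for heart failure, procedure-associated complication, or arrhythmia-related causes". The same section states: "Comparison of the ablation-only registry with the randomized patients will serve as an additional secondary outcome measure". Section 9.3 then says: "Secondary analyses comparing outcomes in the ICD+ablation and ICD arms vs. the registry patients (ablation only) will be performed in a similar manner". The methods it refers back to are Kaplan-Meier estimates, the log-rank test, Cox models and, for VT, this: "The median time to VT recurrence as well as the 95% confidence intervals will be reported for both groups". No separate endpoint, restriction or sensitivity analysis is given for the registry.

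On detection, section 4.5.4 specifies "VT zone 185 or 10 bpm slower than clinical VT (induced or spontaneous) with detection at 30/40 intervals". Section 4.7.1 requires at every visit "ICD Interrogation and event printout".

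**The concern.** One of the two routes to a recurrent-VT event cannot occur in a patient without an ICD. The other depends on somebody recording the rhythm. If the registry is compared with the ICD arms on that definition, fewer counted VT events may mean fewer VT episodes, or simply no device to find and treat them.

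At stake is a named secondary outcome, and with it what the trial will say about ablation alone in patients who decline an ICD. Adjusting a Cox model for baseline covariates deals with differences between patients at entry. It does nothing about an outcome measured by different means in the groups compared.

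**Working it through.** **1. The plan's own figure.** The only design figure is 120 randomized patients (section 9.1: 50% versus 25% at 2 years, 80% power, two-sided 0.05). At 60 per arm the pooled two-proportion formula gives z = (0.25·√60 − 1.96·√(2·0.375·0.625)) / √(0.5·0.5 + 0.25·0.75) = (1.936 − 1.342)/0.661 = 0.90, so power is 0.816. The figure reproduces. It concerns two arms that both have ICDs, and nothing below touches it. No registry size is given.

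**2. Ascertainment side by side.**

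| | ICD and ICD+ablation arms | Registry |
|---|---|---|
| Routes to recurrent VT | appropriate shock or ATP; documented VT >30 s | documented VT >30 s only |
| How VT comes to light | device record read at each visit (4.7, 4.7.1), plus clinical documentation | clinical documentation only |
| 12-lead ECG | baseline (4.7) and before discharge (4.6.1) | none scheduled after discharge; no other rhythm monitoring specified |

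Section 3.6.2 does list device interrogation among the registry visits. The same section defines these patients as having no ICD, and its closing sentence on the 30- and 36-month visits omits interrogation. This is a contradiction to reconcile, not evidence of equal monitoring.

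**3. Duration threshold.** Detection time = intervals × 60 / rate. At 185 bpm, 30 intervals take 30 × 60/185 = 9.7 s and 40 take 13.0 s. ATP can therefore create an event 17 to 20 s before the 30 s threshold that applies in the registry.

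**4. Illustration on VT, registry versus ICD+ablation.** Assumed: equal true 2-year VT risk of 25%; 60 versus 60; exponential times; no dropout; a share m of registry patients with VT never counted, whether too short or undocumented. The documents give no value for m. Counted registry risk p = 0.25(1 − m); HR ≈ ln(1 − p)/ln(0.75); events D = 60(0.25 + p); chance of a significant result favouring the registry ≈ Φ(|ln HR|·√(D/4) − 1.96).

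| m | p | HR | D | Formula | Simulation (8000 runs) |
|---|---|---|---|---|---|
| 10% | 0.225 | 0.89 | 28.5 | Φ(0.32 − 1.96) = 5% | 5.2% |
| 25% | 0.1875 | 0.72 | 26.25 | Φ(0.84 − 1.96) = 13% | 13.1% |
| 50% | 0.125 | 0.46 | 22.5 | Φ(1.82 − 1.96) = 44% | 41.6% |

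The nominal rate in this direction is 2.5%. Varying the true risk from 15 to 35%, or the registry size from 30 to 120, moves the 25% row to about 8 to 17% and the 50% row to about 25 to 60%.

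**5. Same illustration on the composite.** Add death and rehospitalization at 10% per year each (section 9.1), taken as independent. True 2-year risk = 1 − 0.75 × 0.81 × 0.81 = 50.8%. If no missed VT surfaces as another counted event, counted registry risk = 1 − (1 − p) × 0.6561, which is 46.7% at m = 25% and 42.6% at m = 50%. The simulated chance of wrongly favouring the registry is 6.8% and 14.3%. If half of missed VT surfaces as a counted admission or death, it is 4.4% and 7.0%. If all of it does, the rate returns to about 2.5%.

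**6. Precision of a mortality comparison.** At an assumed 10% per year, deaths per group of 60 = 60 × (1 − 0.9²) = 11.4; SE(ln HR) = √(2/11.4) = 0.419; for HR 1.0, the 95% CI is exp(±1.96 × 0.419) = 0.44 to 2.27.

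**The case against.** The strongest reply has five parts.

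- **The comparison is exploratory.** Section 1 uses that language and calls the cohort observational. This limits the reach of the point. But section 9.2 names the comparison as a secondary outcome, and section 9.3 carries the primary methods over to it.
- **No VT log-rank test is named for the registry.** True: for VT alone section 9.3 promises only a median and its interval, and at the assumed 25% risk that median would not be reached by 2 years. A VT test is the natural reading, because the components are secondary endpoints, but it is not explicit. A descriptive VT contrast would carry the same ascertainment difference.
- **Direction is not fixed.** This stands. VT slower than the programmed zone triggers no therapy in the ICD arms either, and VT left untreated may pass 30 s and be documented. If 20% of ICD-arm VT lies below the zone and counts only when documented, the 25% and 50% rows fall to about 10% and 30%; at 40%, to about 8% and 20%. The duration gap matters only for episodes that would have stopped on their own between detection and 30 s, and the documents do not say how common these are.
- **The composite is partly protected.** This stands. Arrhythmia admissions and all deaths count, so some VT missed in the registry will surface there, as may events for which an ICD patient would have been shocked.
- **Equal true risk suits only one comparison.** This stands. Against ICD alone the trial hypothesises a real ablation benefit, so a result favouring the registry need not be wrong. The percentages above do not apply there.

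**Conclusion.** In the secondary registry comparison, recurrent VT is ascertained by different means, and the plan makes no allowance for it. That such a difference exists follows from the documents alone. Its size does not: the 5, 13 and 42% for VT, and the 7 and 14% (none surfacing) or 4 and 7% (half surfacing) for the composite, rest on assumed inputs and concern registry versus ICD+ablation only. The likely direction favours the registry, without certainty.

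A reader might go further in three ways that the documents do not support. One is to infer that the primary result is compromised; both randomized arms have ICDs under the same programming and interrogation rules, so it is not. Another is to infer that the registry will necessarily look better; VT below the zone, untreated VT and differences in true risk could offset or reverse the effect. The third is to infer that the composite cannot be compared at all; its bias is smaller, and nil if every missed VT surfaces as a counted event.

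**What to change.** In sections 9.2 and 9.3:

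1. Report registry recurrent VT descriptively, as a 24-month Kaplan-Meier estimate with 95% CI and a statement that these patients have no ICD, with no formal test against the ICD arms.
2. Make all-cause mortality the main formal registry comparison, labelled observational, with no claim of equivalence.
3. If the composite is still compared, label it observational and add a sensitivity analysis over the share of registry VT not counted.

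In section 3.6.2:

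4. Reconcile device interrogation at registry visits with the absence of an ICD.

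The cost is SAP wording; no new data are needed. The sponsor gives up a formal registry test on VT. What replaces it is imprecise (95% CI about 0.44 to 2.27 around a hazard ratio of 1.0, with 60 per group at an assumed 10% per year) and remains open to self-selection, since patients choose to decline an ICD. Section 1 states that no analysis had been done as of 28 April 2020; a change made before the registry data are analysed would be credible.

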## **10. MONITORING**

Each participating center is responsible for study execution, data collection and monitoring for protocol compliance and conduct. The coordinating site may be consulted regarding any questions specific to protocol conduct.

The coordinating site will collect a copy of the IRB/EC approval letter for each site, as well as a copy of the final approved informed consent before randomization can begin. The coordinating site will collect a final complete data set from each site, and may work with the sites regarding any questions or outstanding data elements.

Upon inspection of the final data set, the coordinating site may request to see source documentation, reports of protocol deviations or adverse events if needed to verify data elements.

## **11. INSTITUTIONAL REVIEW BOARD AND ETHICS COMMITTEE**

The study protocol must be reviewed and approved by the appropriate Institutional Review Board/Ethics Committee before subject enrollment may begin. Proposed changes to the protocol must be reviewed by the coordinating site PI and significant changes must be approved in writing as well as the Institutional Review Board / Ethics Committee. A significant change is one which may increase risks or present a new risk to the subject, or which may adversely affect the scientific validity of the study. Each investigator must sign the protocol amendment before implementing the change at his/her center.

IRB/EC approval is required for each institution participating in this investigation. Prior to enrollment, a signed copy of the Institutional Review Board approval letter addressed to the investigator must be submitted to the coordinating site certifying study approval. Investigators are responsible for obtaining and maintaining approval of the study by the IRB/EC. Annual review and approvals for continuation of the trial at each center must also be forwarded to the lead site where they will be submitted to coordinating site's IRB at the time of continuing review, per IRB policy. Correspondence with the IRB/EC should be retained at the center. Adverse events and protocol deviations must be reported per IRB/EC requirements.

## **12. STATEMENT OF COMPLIANCE**

The clinical investigation shall be conducted in accordance with the ethical principles that have their origin in the Declaration of Helsinki and ISO 14155.

These principles protect the rights, safety, and well-being of human subjects, which are the most important considerations and shall prevail over interest of science and society. These principles shall be understood, observed, and applied at every step in the clinical investigation.

Protocol required investigational activities shall not begin until the required approval, or favorable opinion from the Institutional Review Board (IRB) or Ethics Committee (EC) or regulatory authority has been obtained and any additional requirements imposed by the IRB or EC or regulatory authority shall be followed.

